4.7 Determination of Sample Size

The sample size for the study was calculated assuming an effect size of 0.51 on both endpoints between active treatment and placebo. Controlling the overall type I error rate at 10% for the study, each endpoint will be tested at a two-sided alpha of 5% (equivalent to 2.5% one-sided) considering that a significantly larger decrease compared to placebo in either endpoint will be considered sufficient for study success. A power of approximately 80% for each endpoint is achieved with 62 patients completing the study in each arm, active treatment, and placebo. Accounting for a drop-out rate of 20%, 78 patients (total 156 patients) should be recruited per arm. A sample size adjustment will be considered at the interim analysis (see Section 9.6).

The original sample size adjustment above controls the overall type 1 error rate at 10%. However, to meet the requirements for proof of registration, the alpha was adjusted to control for a type 1 error rate of 5%, split evenly between the two endpoints. Assuming an effect size of 0.51 (mean 510, standard deviation 1000) a sample size of 150 completers (75 per arm) is required for 80% power at a two-sided alpha of 0.025 for each endpoint. Assuming 20% dropout would require 188 patients enrolled.

4.8 Interim Analyses

An interim analysis will be conducted after 90 patients have completed their *Week 10* evaluations (expected 108 patients enrolled after accounting for 20% dropout). Individuals that had the opportunity to complete their Week 10 visit but were lost to follow-up will also be included in the analysis, however, will not be included in the 90-patient count required for interim analysis initiation. In addition, unblinded safety outputs will be produced. After the patient count requirement for interim analysis has been reached, sufficient time will be allowed for data cleaning, data transfers (including laboratory) and medical coding.

The interim analysis will be conducted as per the main efficacy analysis described in Section 5.1.13. Sensitivity analyses will not be performed.

A sample size adjustment will be performed using the promising zone approach as described by Mehta and Pocock ([1]) which allows the sample size to be adjusted based on an interim analysis only if the data are in a promising zone, i.e., the effect is trending toward success but not strong enough to indicate it will finish successfully without increasing the sample size. If the effect is

strong (favorable zone) or too weak (unfavorable zone) the trial will be allowed to accumulate participants to the originally planned sample size (188 enrolled; 150 anticipated completers). If data are within the promising zone, the sample size will be increased in a stepwise fashion to keep the estimated power of the study between 80 and 85%. This step wise approach to increasing sample size at interim is implemented to avoid the possibility of back calculating the observed effect size from the sample size increase, although variations in standard deviation and placebo decline rates from historical expectations already make this difficult.

As Mehta and Pocock assess single outcomes, we interrogated control of the type I error rate using dual outcomes as proposed in this SAP. The code to generate the simulation and results showing that this approach effectively controls type I error in a Promising Zone simulation can be found in the attached document `promising_zone_simulation.R`. Images produced with this code can be found in Appendix 7.2.

[figure not shown]

Figure 2. Promising Zone. The promising zone boundaries (orange box) and corresponding sample size increases are detailed above. The solid black line corresponds to the proposed enrolled (right; y-axis) and completer (left; y-axis) sample sizes relative to the test statistic (x-axis) observed at interim. Sample sizes were calculated using an 80-85% power threshold to provide binning for sample size increase, thus avoiding back calculation of the effect size at interim. Unfavorable and favorable zones are shaded in grey and blue, respectively.

The conditional power at interim, or probability of study success, for detecting the difference in primary outcome between the two groups in the final analysis, will be estimated using the accumulated data. The proposed starting sample size of 90 study participants results in 85% power for both primary outcomes (assuming a Cohen's D of 0.51). We have elected to begin the study

with the expected sample size estimate and adjust upward if improvement in the treated cohort does not resemble what was observed in the previous studies.

The promising zone will increase the sample size to maintain 80% to 85% power to detect a significant effect, i.e. if the power goes below 80% the sample size will be increased to achieve power between 80% and 85% (Table 1; Figure 2). Development of the 80-85% thresholds also maintain blind of the interim results. If at interim the test statistic is in the favorable zone (≥ 1.944) the study will proceed as originally described (150 completers). If at interim the test statistic falls within the promising zone (test statistic: $< 1.944 \geq 1.412$), sample size adjustment will follow the test statistic ranges outlined in Table 1 and Figure 1. If the test statistic is less than 1.412 (40% conditional power at interim) the sample size will not be increased (remain at 150 completers). The lower bound of the promising zone (effect size 0.23) is set by sample size constraints, however clinically meaningful effects have been observed at an effect size as low as 0.2. The study will be stopped for futility if the test statistic falls below a 50% probability (conditional power) of observing a result favoring *placebo*. This corresponds to a test statistic below -1.987 (effect size equal to -0.4177).

At interim analysis two discontinued individuals reached visit 6, and were included in the IA analysis. The table below was adjusted for 92 individuals worth of information, as opposed to the 90 individuals mentioned above.

Table 1. Promising Zone Thresholds

	Test Statistic at Interim	Completers	Sample Size (total Enrollment)
Futility	$-\infty < Z \leq -1.987$	N at time of futility declaration	--
Unfavorable Zone	$-1.987 < Z < 1.412$	150	188
Promising Zone	$1.412 \leq z < 1.555$	300	376
	$1.555 \leq z < 1.649$	265	332
	$1.649 \leq z < 1.745$	231	290
	$1.745 \leq z < 1.845$	201	252
	$1.845 \leq z < 1.944$	174	218
Favorable Zone	$1.944 \leq z < \infty$	150	188

Sample size calculations will be generated as described below. The more conservative sample size calculation between the two primary efficacy endpoints will be used.

The following formulas will be used:

$$CP(z_1, \tilde{n}_2) = 1 - \Phi \left(\frac{z_\alpha \sqrt{n_2} - z_1 \sqrt{n_1}}{\sqrt{\tilde{n}_2}} - \frac{z_1 \sqrt{\tilde{n}_2}}{\sqrt{n_1}} \right)$$

$$\tilde{n}_2' = \left(\frac{n_1}{z_1^2} \right) \left(\frac{z_\alpha \sqrt{n_2} - z_1 \sqrt{n_1}}{\sqrt{n_2} - n_1} + z_\beta \right)^2$$

Here:

- z_1 is the Wald-statistic observed at the interim analysis,

- α is the *one-sided* significance level of the test (here 2.5%),
- z_{α} is the corresponding critical value of the normal distribution,
- n_2 is the total number of patients originally planned,
- \tilde{n}_2 is the incremental number of patients $n_2 - n_1$,
- \tilde{n}_2' is the proposed new incremental number of patients,
- β is 1 - statistical power, and
- Φ is the cumulative density function of the normal distribution.

Note: \tilde{n}_2' will only be calculated if CP is in the promising zone. Both n_2 and the adapted sample size $n_2' = n_1 + \tilde{n}_2'$ are adjusted for the expected drop-out rate, i.e., the n_2 is considered to be 150 and $n_2 / 0.8$ patients (rounded up to an even number) will be recruited after adaptation of the sample size.

If the CP for both endpoints is below 40%, the study will be continued without modifications.

Details for the safety deliverables are described in Section 5.2.11.

All analyses at interim will be conducted by a separate unblinded statistical team.

The decision tree for promising zone can be found in appendix 7.3.

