9.4. Determination of Sample Size

The sample size for the study was calculated assuming an estimand of the effect size between active treatment and placebo of 0.51 on both endpoints, considering the placebo effect will not exceed the 30%.

The Phase IIa REIMAGINE trial did not contain a placebo group to further help establish the estimand. Moreover, there is no 'gold standard' measure in BPD clinical development, thus, there is no historical clinical trial data on the COAs proposed in PORTICO to establish a more accurate estimand.

Controlling the overall type I error rate at 5% for the study, both endpoints will be tested at a two-sided alpha of 2.5%. A power of approximately 80% for each endpoint is achieved with 75 patients completing the study in each arm, active treatment and placebo. Accounting for a drop-out rate of 20%, 94 patients (total 188 patients) should be recruited per arm. A sample size adjustment will be considered at the interim analysis (see Section 9.6). The total sample size will not be increased to more than 300 completed patients.

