9.6. Interim Analysis

An interim analysis will be performed after 90 participants have completed the specific week assessments (expected 108 patients enrolled after accounting for 20% dropout). Individuals that had the opportunity to complete their specific week visit, but were lost to follow-up, will also be included in the analysis, however, will not be included in the 90-patient count required for initiation of the interim analysis. The objective of this interim analysis will be to reassess the sample size based on the observed variability and effect sizes. The interim analysis will be conducted as per the main efficacy analysis. Imputation and sensitivity analyses will not be performed. A sample size adjustment may be performed using the promising zone approach as described by Mehta and Pocock which allows the sample size to be adjusted based on an interim analysis only if the data are in a promising zone, i.e., the effect is trending toward success but not strong enough to indicate it will finish successfully without increasing the sample size (Mehta & Pocock, 2000). If the effect is strong (favorable zone) or too weak (unfavorable zone) the trial will be allowed to accumulate participants to the originally planned sample size (188 enrolled). If data are within the promising zone, the sample size will be increased in a stepwise fashion to keep the estimated power of the study between 80 and 90%. This step wise approach to increasing sample size at interim is implemented to avoid the possibility of back-calculating the observed effect size from the sample size increase, although variations in standard deviation and placebo decline rates from historical expectations already make this difficult. For both primary endpoints, a new sample size will be determined independently. This will yield two proposed new sample sizes, one per endpoint. The larger proposed increase will be used.

Additional details will be provided in the SAP which will be finalized prior to conduct of the interim analysis.

At the interim analysis, the safety data will also be reviewed by the DMC.

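### SAP 4.8 states 80–85% power throughout the promising zone, but the capped 300-completer step starts at about 76% and reaches 80% only at an interim z of 1.473

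*SAP*

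**What the plan says.** SAP 4.8 makes the power claim more than once. When the data are in the promising zone, "the sample size will be increased in a stepwise fashion to keep the estimated power of the study between 80 and 85" per cent. After Figure 2 it repeats: "The promising zone will increase the sample size to maintain 80% to 85% power to detect a significant effect", and spells this out as "if the power goes below 80% the sample size will be increased to achieve power between 80% and 85% (Table 1; Figure 2"). The legend of Figure 2 gives the same 80–85% threshold as the basis for the sample sizes.

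Table 1 assigns completer totals by interim z: 300 for 1.412 to 1.555, 265 for 1.555 to 1.649, 231 for 1.649 to 1.745, 201 for 1.745 to 1.845, and 174 for 1.845 to 1.944. Outside the promising zone, short of futility, the total stays at 150.

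The SAP describes z = 1.412 in two ways: as the point of 40% conditional power, and as a bound set by sample size constraints. Just above Table 1 it reports that two discontinued participants were included in the interim analysis, and adds: "The table below was adjusted for 92 individuals worth of information, as opposed to the 90 individuals mentioned above".

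Protocol 9.6 gives a wider band: "the sample size will be increased in a stepwise fashion to keep the estimated power of the study between 80 and 90" per cent. Protocol 9.4 sets the cap: "The total sample size will not be increased to more than 300 completed patients".

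**The concern.** Two separate constraints fix the first promising-zone step. Its lower edge is where conditional power at the planned 150 completers is 40%. Its size is the cap of 300 completers. Nothing guarantees that 300 completers are enough for 80% power at that edge, yet the text promises 80–85% for the whole zone.

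This is the largest adaptation in the plan: completers double from 150 to 300 and enrolment goes from 188 to 376. A sponsor or monitoring committee reading SAP 4.8 would take that expansion to carry at least 80% conditional power wherever the interim result falls in the step. If it does not, the plan states a power that the design lacks at its most expensive point.

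**Working it through.** **Inputs.** Interim information n1 = 92 (SAP 4.8, note above Table 1). Planned total n2 = 150 completers and one-sided α = 2.5%, so z_α = 1.960 (SAP 4.8, definitions under the formulas). Row sizes and z limits come from Table 1.

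**Formula.** This is the SAP's conditional power (CP) under the observed trend, with final total N:

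CP(z1, N) = 1 − Φ[ (z_α√N − z1√n1)/√(N − n1) − z1√(N − n1)/√n1 ]

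**1. Zone limits reproduce (N = 150).**
- z = 1.412: (1.960 × 12.247 − 1.412 × 9.592)/7.616 = 1.374, and 1.412 × 7.616/9.592 = 1.121. CP = 1 − Φ(0.253) = 40.0%.
- z = 1.944: the same steps give 80.0%.
- With n1 = 90 these would be 41.4% and 80.8%, so 92 is the right input.

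**2. The other four promising-zone rows reproduce.**

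| Completers | CP at lower z | CP at upper z |
|---|---|---|
| 265 | 80.0% | 85.0% |
| 231 | 80.0% | 85.0% |
| 201 | 80.0% | 85.1% |
| 174 | 80.0% | 85.1% |

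**3. The 300-completer row does not.** At z = 1.412: (1.960 × 17.321 − 1.412 × 9.592)/14.422 = 1.415, and 1.412 × 14.422/9.592 = 2.123. CP = 1 − Φ(−0.708) = 76.1%. Across the step:

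| Interim z | CP at 300 completers |
|---|---|
| 1.412 | 76.1% |
| 1.430 | 77.3% |
| 1.450 | 78.5% |
| 1.473 | 80.0% |
| 1.500 | 81.6% |
| 1.555 | 84.6% |

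The 80% crossing is at z = 1.4735. The share of the step below it is (1.4735 − 1.412)/(1.555 − 1.412) = 0.0615/0.143 = 43%. The largest shortfall is 80 − 76.1 = 3.9 points, and it exceeds 2 points only for z below about 1.441.

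**4. Other readings at one-sided 2.5%.** The SAP's second formula, as printed, keeps the critical-value term at n2 = 150. On that reading the 300 step starts at 77.3% and crosses 80% at z = 1.445. However, the other four rows then run from about 82% to 88%, so Table 1 was evidently not built that way. With n1 = 90 and the formula above, the step starts at 77.0% and crosses at 1.459. Each reading leaves the lower end of the step under 80%.

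**5. Cause.** Solving CP(1.412, N) = 0.80 gives N = 330.1, that is 331 completers; 85% needs 378. Both exceed the cap of 300. Under the printed second formula, 80% needs 318.4, which also exceeds it.

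**The case against.** The strongest reply is that the gap is small, seldom reached and partly disclosed.

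- **Size.** Averaged evenly over z, conditional power is 78.1% in the affected part of the step and 80.5% over the whole step. With n1 = 92 and the design effect of 0.51, an endpoint's interim z has mean 0.51 × √92/2 = 2.446. The chance that it falls between 1.412 and 1.4735 is then about 1.5%, and it is at most about 2.5% for any true effect from 0 to 0.51. Conditional power under the observed trend is itself a noisy estimate. This stands, and it limits the weight of the point.
- **Disclosure.** SAP 4.8 attributes the lower bound to sample size constraints, and protocol 9.4 states the cap. This stands only in part. Neither sentence says that the 80% floor is given up, and a bound set jointly by the cap and 80% conditional power would be about 1.473, not 1.412.
- **The two bands.** The protocol's 80–90% and the SAP's 80–85% share the same floor, and the protocol leaves further detail to the SAP. Aligning them is tidying, not a second error.

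A reader might infer something stronger by noting that an endpoint that succeeds alone under Hochberg must meet one-sided 1.25%, where the 300 step gives only 64–75%. That figure says nothing about the cap. At 1.25% all the other promising-zone rows also fall below 80%, to between about 67% and 75%. It follows from the choice of α in the conditional-power formula, which is a separate point.

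**Conclusion.** The statement in SAP 4.8 is wrong as written for one row of Table 1. At 300 completers, conditional power runs from 76.1% to 84.6%, and it is below 80% for interim z from 1.412 to 1.473. The part of the step above 1.473 meets the stated band, as do the other four rows.

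The result rests on the SAP's own inputs (n1 = 92, one-sided 2.5%, conditional power under the observed trend). The exact crossing point depends on how the formulas are read, but the shortfall at the lower edge does not.

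The documents do not support reading this as a type I error problem, since nothing in this point alone affects the error rate. Nor do they support a claim that the 300-completer expansion is seriously underpowered throughout. It is a power figure that needs a caveat: modest in size, and worth correcting because it describes the costliest adaptation and the correction is cheap.

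**What to change.** In SAP 4.8, amend both statements of the 80–85% target and the legend of Figure 2. Say that the 300-completer step is limited by the cap and gives about 76–85% conditional power at one-sided 2.5%, while the other promising-zone steps give 80–85%. Make the matching change in protocol 9.6 and use the same band in both documents.

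Do not raise the lower boundary to 1.473, although 300 completers would then deliver 80% everywhere in the step. The SAP already reports who was included at the interim and that Table 1 was recalculated for them. Moving a threshold now would change the adaptation rule after the interim data cut.

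The cost is a few sentences in each document and a slightly less favourable stated power. No threshold, sample size or analysis changes.

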The random effect of subject will be accounted for via the within-subject error correlation structure. The preferred covariance structure for the model will be unstructured (UN in SAS). If this analysis fails to converge, the model will be simplified first to Heterogeneous Toeplitz (TOEPH), then first order autoregressive with heterogeneous variance (ARH1), then compound symmetry with heterogeneous variance (CSH), followed by compound symmetry (CS). The first (co)variance structure yielding convergence will be used as the primary analysis. If a structured covariance matrix is used the sandwich estimator will be implemented to account for potential correlation matrix misspecification. The degrees of freedom will be calculated using the general Kenward-Roger approximation.

The SAS code for the primary analysis is as follows:

```
PROC MIXED data=adqs;
CLASS TRT01P(REF='Placebo') AVISITN(REF='3') SITEGR1(REF='01') PSYBLFL USUBJID;
MODEL CHG= SITEGR1 AVISITN TRT01P AVISITN*TRT01P STDBASE STDBASE*AVISITN PSYBLFL
STDBASE*PSYBLFL /s SOLUTION CL DDFM = KenwardRoger;
REPEATED AVISITN/ SUBJECT= USUBJID TYPE=UN;
LSMEANS TRT01P*AVISITN /at STDBASE=0 PDIFF CL;
ESTIMATE \see below\
Run;
```

Estimates statements averaging visits 6-8 are as follows:

Vafidemstat LSMEANS

```
ESTIMATE 'TRT01P{Vafidemstat} AVISITN{AVG 6-8}'
INTERCEPT 1
AVISITN 0 0 0.33333 0.33333 0.33333 0
TRT01P 1 0
AVISITN*TRT01P 0 0 0.33333 0.33333 0.33333 0 0 0 0 0 / e cl;
```

Placebo LSMEANS

```
ESTIMATE 'TRT01P{Placebo} AVISITN{AVG 6-8}'
INTERCEPT 1
AVISITN 0 0 0.33333 0.33333 0.33333 0
TRT01P 0 1
AVISITN*TRT01P 0 0 0 0 0 0 0 0.33333 0.33333 0.33333 0 / e cl;
```

LSDiff (Vafidemstat – Placebo)

```
ESTIMATE 'TRT01P{Vafidemstat} AVISITN{AVG 6-8} _TRT01P{Placebo} _AVISITN{AVG 6-8}'
TRT01P 1 -1
AVISITN*TRT01P 0 0 0.33333 0.33333 0.33333 0 0 0 -0.33333 -0.33333 -0.33333 0 / e cl;
```

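### SAP 4.8 labels its futility boundary of -1.987 as 50% conditional power, but the SAP's own formula makes it about 82%; the 85% power stated for 90 participants is also wrong

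*SAP*

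**What the plan says.** SAP 4.8 gives a futility rule in words and then a number for it:

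- The rule: "The study will be stopped for futility if the test statistic falls below a 50% probability (conditional power) of observing a result favoring" placebo.
- The number: "This corresponds to a test statistic below -1.987 (effect size equal to -0.4177"). Table 1 repeats -1.987 as the futility limit and is said to have been adjusted to 92 participants' worth of information.

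The section also states: "The proposed starting sample size of 90 study participants results in 85% power for both primary outcomes", at a Cohen's d of 0.51.

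On whether a futility stop exists, the documents differ:

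- Protocol 9.6 has none. An effect that is strong "or too weak (unfavorable zone) the trial will be allowed to accumulate participants to the originally planned sample size".
- The end of SAP 4.8 says that the study carries on unchanged if conditional power is under 40% for both endpoints.
- SAP 4.8 (text and Table 1) and Appendix 7.3 do stop for futility; Appendix 7.3 requires both endpoints to be below the limit.
- SAP 5.5 reports no departure from the protocol's planned analysis.

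Three lesser statements belong here: "The lower bound of the promising zone (effect size 0.23) is set by sample size constraints" (SAP 4.8); "expected 108 patients enrolled after accounting for 20% dropout" (Protocol 9.6, repeated in SAP 4.8); and the coded treatment contrast in SAP 5.1.1, labelled "LSDiff (Vafidemstat – Placebo").

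**The concern.** A stopping rule stated both in words and as a number must give the same answer either way. If a result favouring placebo means a significant one, an interim Z between -1.987 and -1.535 on both endpoints meets the verbal rule but not the tabulated one. The data monitoring committee and the unblinded statistician would then have two incompatible instructions, while Protocol 9.6 gives a third, which is not to stop.

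The 85% power figure triggers no action, but it tells the reader that the interim sample alone is nearly sufficient. SAP 4.7 contradicts this: it needs 150 completers for 80% power at two-sided 2.5%, and needed 62 per arm (124) for about 80% under the superseded two-sided 5% per endpoint.

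**Working it through.** **Inputs.** n1 = 92 (SAP 4.8, above Table 1; 90 before that adjustment), n2 = 150, one-sided alpha 2.5% so z_a = 1.960 (SAP 4.8), d = 0.51 (SAP 4.7), 1:1 allocation (SAP 3.1).

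**1. Reproduce the plan's own limits.** The SAP 4.8 formula is

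CP = 1 - Φ[ (z_a√n2 - z1√n1)/√(n2 - n1) - z1√(n2 - n1)/√n1 ],

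with √150 = 12.247, √92 = 9.592, √58 = 7.616.

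- z1 = 1.412: (24.005 - 13.544)/7.616 - 1.412 × 0.794 = 1.374 - 1.121 = 0.253, so CP = 40.0%, as the SAP states.
- z1 = 1.944: 0.704 - 1.544 = -0.840, so CP = 80.0%, matching the SAP's 80% threshold.

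This is therefore the formula behind the promising zone.

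**2. Apply it, mirrored, to the futility limit.**

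- |z1| = 1.987: (24.005 - 19.059)/7.616 - 1.987 × 0.794 = 0.649 - 1.578 = -0.928, so CP = 82.3% (83.1% with n1 = 90).
- Setting the bracket to zero gives the 50% point: |z1| = z_a√(n1/n2) = 1.960 × √(92/150) = 1.535.
- At one-sided 1.25%, the level for one endpoint alone under Hochberg, CP at -1.987 is 68.3% and the 50% point is -1.755.

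Other definitions do not give 50% at -1.987 either: about 26% under zero drift for the remaining data, 77% predictive power, and above 99.9% for a merely negative final Z under the current trend.

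**3. Where -1.987 and -0.4177 come from.** The two-sided 5% t critical value is 1.9873 on 88 df and 1.9867 on 90 df. The effect size with exactly 50% power in a two-sided 5% t-test at 45 per arm is 0.41776. The pair therefore matches 50% stand-alone power at the interim sample size. The d belongs to 90 participants; with 92, Z = -1.987 is d = -2 × 1.987/√92 = -0.414.

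**4. Power with 90 participants.** The noncentrality is 0.51 × √(45/2) = 2.419.

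| Two-sided alpha | Normal | Noncentral t |
|---|---|---|
| 5% | 67.7% | 66.7% |
| 2.5% | 57.1% | 55.7% |

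The design itself reproduces: 75 per arm at two-sided 2.5% gives 81.1% (normal) or 80.4% (t). Power of 85% needs about 70 per arm at 5% or 83 per arm at 2.5%. Reading 90 as per arm gives 88.1% at 2.5% and 92.8% at 5% (normal).

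**5. Lesser figures.**

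- Effect at Z = 1.412: 2 × 1.412/√92 = 0.294; on 150 it is 2 × 1.412/√150 = 0.231. The just-significant effect at the 300-completer cap is 2 × 1.960/√300 = 0.226.
- Enrolment for 90 completers: 90/0.8 = 112.5, so 113 by the rule that turns 150 into 188; 90 × 1.2 = 108. Linear dropout to Week 10 gives 90/(1 - 0.20 × 10/12) = 108, or 90/(1 - 0.20 × 10/14) = 105.

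**The case against.** **The 82% depends on reading a result favouring placebo as a significant one.** SAP 4.8 does not say so. But a merely directional reading puts the 50% point at Z = 0 under the current trend, further from -1.987. The ambiguity is one more thing to resolve and does not rescue the number.

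**A figure near 85% can be found.** The chance that at least one endpoint reaches an unadjusted two-sided 5% with 45 per arm is 85.6% if the endpoints correlate at 0.3. That needs an unstated correlation and the superseded 10% overall error rate, and it is not power for each endpoint. Under the current Hochberg rule the chance of success on at least one endpoint is at most 82.8% (independent endpoints).

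**The protocol defers interim details to the SAP, and Protocol 10.4.1 lets the committee recommend termination.** That is fair, and it softens the protocol gap. It does not remove the conflict inside SAP 4.8 or with SAP 5.5.

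A reader might go further than the documents allow:

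- *That 0.23 is an arithmetic error.* It reproduces on 150 completers (0.231) or at the 300 cap (0.226), and the latter fits the SAP's reference to sample size constraints. The defect is that the sample size is unstated and differs from the one behind -0.4177.
- *That 108 is wrong.* The trigger is Week 10, and lower dropout by then can give 108. The assumption is missing; the figure is not refuted.
- *That a strong benefit would fall in the futility row*, because lower scores are better and the coded contrast is vafidemstat minus placebo. SAP 4.8 ties negative values to results favouring placebo, so the intent is clear; only an explicit sign statement is missing.

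**Conclusion.** Wrong as written. The futility limit is labelled 50% conditional power, but on the SAP's formula and alpha it is about 82% for a significant placebo win; the matching 50% point would be -1.535. The 85% power with 90 participants should read 67% (two-sided 5%) or 56% (two-sided 2.5%).

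The consequences are limited. Appendix 7.3 recommends the stop only if both endpoints cross; a stricter futility limit cannot inflate type I error; and 1.412 and 1.944 are correct at the stated alpha. As an illustration with assumed inputs, if the true effect were -0.2 on both endpoints, the joint stop would fire in about 6% of trials at -1.987 against 14% at -1.535 when the endpoints correlate at 0.5 (2% against 8% at correlation 0; 11% against 22% at 0.9). With no true effect the figures run from 0.1% against 0.4% to 1.4% against 4.1% over the same correlations.

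A reader might infer that the limit should now be moved to -1.535. SAP 4.8 reports in the past tense which discontinued participants entered the interim analysis. Moving the limit would then change a decision threshold after the look.

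**What to change.** - **Futility limit.** Keep -1.987. Describe it as an interim result significantly favouring placebo at two-sided 5%, equal to about 82% conditional power of a significant placebo win by the SAP formula, and update the effect size to -0.414 for 92 participants. Use -1.535 only if no interim result had been seen. Define whether a result favouring placebo means a significant one.
- **Power.** Replace 85% by 67% (two-sided 5%) and 56% (two-sided 2.5%).
- **Futility stop.** Make Protocol 9.6, the SAP 4.8 text and Table 1, the SAP 4.8 sentence on conditional power below 40%, Appendix 7.3 and SAP 5.5 agree on whether the stop exists. If it does, say in SAP 4.8 that both endpoints must cross.
- **Clarifications.** State the sample size behind 0.23, noting that an observed interim effect at Z = 1.412 with 92 participants is 0.29. State the Week 10 dropout assumption behind 108, noting 113 under the N/0.8 rule. State that positive Z means benefit, the reverse of the coded contrast.

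The cost is wording in SAP 4.8 and 5.5 and a line in Protocol 9.6. No operating threshold changes, though the stated power becomes less favourable.
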